#### *Statistical Power and Sample Considerations*

The number of subjects included in the study will be based on a compassionate use protocol and not on study power considerations. The primary safety analysis will be descriptive and not based on statistical significance. However, in Table 4 we outline power to detect several differences in the frequency of adverse events, assuming 20, 25, or 30 patients, diverse proportion of subjects with adverse event in either treatment period and not with the adverse event in either treatment period and not with the adverse event in the other (proportion of discordant pairs), for a two-sided 5% significance level McNemar's tests.

For lower proportions of discordant pairs, we would generally attain close to 80% power in McNemar's test. Even for higher proportions of discordant pairs, assuming the high differences between before and after treatment that we expect to observe, e.g., 50% or more, 80% power can be attained in McNemar's test (Table 4).

Table 4—Power to detect varying differences in proportions before and after treatment with Omegaven® in a McNemar's test. All calculations based on an alpha significance level of 0.05

Difference between proportions	Proportion of discordant pairs	McNemar's Test		
		Sample Size		
		20	25	30
30%	40%	59%	72%	81%
	60%	44%	55%	63%
50%	60%	92%	97%	99%
	80%	79%	88%	93%
80%	85%	>99%	>99%	>99%
	95%	>99%	>99%	>99%

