### Outcome/Endpoints

#### *Treatment safety*

Our primary outcome for treatment safety will be based on patient's essential fatty acid profile. We will compare patients before treatment with Omegaven® started and after treatment started (one month after treatment started until treatment stopped) with respect to the frequency with which triene/tetraene ratio  $> 0.2$  at any time. Primary analyses for these and all other safety outcomes will be based on a follow-up time for Omegaven® starting 30 days after baseline, i.e., 30 days after treatment started for Omegaven® patients and 2 months after the first direct bilirubin level  $< 2$  mg/dL was recorded.

Additional comparisons across treatment periods for subjects receiving Omegaven® will be aimed to assess occurrence of spontaneous bleeding (e.g., unexplained bruising, oozing from gums/incision sites), and maximum triene/tetraene ratio, minimum platelets, maximum international normalized ratio (INR), and trends in pre-albumin (age standardized levels). We will also explore trends in coagulopathies based on curves of platelets, prothrombin time (PT), partial thromboplastin time (PTT) over time, and INR. We will also describe the rate with which INR ratios were  $> 2$  (number of days/follow-up time), as a marker of coagulopathies.

Additional evaluation of Omegaven® will be performed with regards to rate in which albumin is  $> 3$  g/dL, maximum triglyceride level, rate of blood stream infections (number of positive blood cultures/follow-up-time under PN after baseline), rate of central venous catheter (CVC) infections (number of CVC infections/follow-up time and number of gram positive CVC infections/follow-up time), and occurrence of anaphylactic reactions after baseline.

We will describe trends over time for all outcomes associated with fatty acid profiles (including triene/tetraene ratios, triglycerides, total omega-6 fatty acids, total omega-3 fatty acids, total saturated, total monounsaturated, and total polysaturated fatty acids). Specific fatty acids such as arachidonic, palmoleic, palmitic, oleic, stearic, and linoleic fatty acids will also be evaluated and described.

[name], Department of Surgery, Children's Hospital & Medical Center  
[name], Department of Surgery, Children's Hospital & Medical Center  
[name], Pediatric Research Office, Dept. of Pediatrics, UNMC  
[name], Department of Biostatistics, College of Public Health, UNMC

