#### **G. Adverse Event Criteria and Reporting Procedures**

Adverse events (AEs) will be assessed and reported from the time of the first Omegaven® infusion until exit from the study in accordance with UNMC Pediatric IRB reporting requirements. In particular, the patient will be observed during and shortly after Omegaven® administration for the occurrence of anaphylactic or allergic reactions. Other expected adverse events include death, blood stream infection; transfer to ICU for treatment of respiratory distress or hemodynamic instability; re-hospitalization for treatment of blood stream infection, dehydration, electrolyte abnormalities, catheter malfunctions, bowel obstructions, and urinary tract infection. Unexpected adverse events will also be assessed and reported in compliance with the UNMC Pediatric IRB requirements. Patients experiencing any adverse events that are moderate or severe in nature and that may be related to Omegaven® will have their treatment temporarily halted until the adverse event has resolved. Dose modifications will occur as described above. If a dose reduction is made for adverse events later considered to be unrelated to Omegaven®, the Omegaven® dose will be increased back to the dose prescribed prior to the dose reduction. Patients with anaphylactic or allergic reactions will not continue Omegaven® treatment.

Any serious or unsuspected adverse events will be reported to the IRB and the FDA within 72 hours of the occurrence being known, or immediately if the event is fatal or life threatening as per UNMC Pediatric IRB Policy on Adverse and Unexpected Events and Unanticipated Risks to Research Subjects and Others. This will be done in person, by telephone, or email, and by completion of the IRB's form for adverse/unexpected event reporting.

Adverse events are detected by Children's Hospital & Medical Center acute care medical and nursing staff during provision of standard care services including the routine monitoring of vital signs and daily physical exam data. Adverse events identified by Children's Hospital & Medical Center staff are reported to the Principal Investigator immediately by telephone or pager, and subsequently to the appropriate board or committee.

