### *Analysis of Safety and Tolerability of Omegaven®*

All primary safety and tolerability analyses will be based on descriptive statistics. In secondary analyses, we will also assess the statistical significance of differences. The period receiving Omegaven® will start 30 days after beginning PN with Omegaven® for the main analysis. Outcomes measured in the Omegaven® will be described for a period starting 30 days after baseline.

Primary outcomes measured will include whether the triene/tetraene ratio was ever  $> 0.2$  during the intervention period and whether the INR was ever  $> 2$ . Secondary outcomes measured will include platelets, prothrombin time (PT), partial thromboplastin time (PTT), and other components of the fatty acid profile. Analysis of all categorical outcomes will be based on proportions and of all continuous outcomes will be based on means or medians of the individual mean, maximum or minimum values, as appropriate, during the respective follow-up period. Comparisons between periods (pre and post-treatment) will be performed based on paired tests, parametric or non-parametric, as appropriate. We will also explore trends over time (e.g., decreasing for INR and increasing for pre-albumin) and estimate p-values via regression models using generalized estimating equations or random effects to account for within subject correlations. When describing outcomes over time, we will explore the effect of predictors of poor hepatic outcomes, such as use of antifungal agents (e.g., amphotericin) and antidiarrheal agents (e.g., loperamide), on potential spikes.

[name], Department of Surgery, Children's Hospital & Medical Center  
[name], Department of Surgery, Children's Hospital & Medical Center  
[name], Pediatric Research Office, Dept. of Pediatrics, UNMC  
[name], Department of Biostatistics, College of Public Health, UNMC

We will also evaluate nutritional outcomes including difference in weight-for- age Z-scores and height-for-age Z-scores from baseline to the moment in which the child starts enteral feeding and to the moment in which the child receives less than 10% of their calories from PN. Using linear regression, we will explore adjustment for baseline alternative predictors of interest. Trends over time in Z-scores will also be explored using regression with repeated measure methods.

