**Side effects:**

The infusion of Omegaven® can lead to a prolonged bleeding time and an inhibited platelet aggregation. In rare cases, patients may experience a fishy taste.

The administration of Omegaven® should be stopped or reduced if there is a marked increase in blood glucose levels during the Omegaven® infusion. Undesirable effects that are seen during the infusion of Omegaven® that may also occur with conventional fat emulsions (i.e. Intralipid®) include:

Slight rise in body temperature  
Heat sensation and/or cold sensation  
Chills  
Flushing or cyanosis  
Lack of appetite, nausea, vomiting  
Dyspnea  
Headache, pain in the chest, bone pain  
Priapism  
Increase/decrease in blood pressure  
Anaphylactic reactions/erythema

Other expected adverse events that are common to all patients with short bowel syndrome, regardless of the type of fat emulsion they receive, include blood stream infections and re-admittance to hospital. Causes for re-hospitalization include dehydration, bloodstream infections, electrolyte abnormalities, bowel obstruction, and central venous catheter malfunction.

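### Table 4 gives before/after McNemar power for adverse events, but the plan sets no pre-treatment collection of clinical events, and laboratory outcomes are sampled unequally in the two periods

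*Protocol*

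**What the plan says.** **The power statement.** Under Statistical Power and Sample Considerations the protocol says that "in Table 4 we outline power to detect several differences in the frequency of adverse events, assuming 20, 25, or 30 patients". The table's caption describes the contrast as "Power to detect varying differences in proportions before and after treatment with Omegaven® in a McNemar's test", and the text gives the test "for a two-sided 5% significance level McNemar's tests". The same section expects large effects: "assuming the high differences between before and after treatment that we expect to observe, e.g., 50% or more". It also says that enrolment follows a compassionate use protocol rather than power, and that the primary safety analysis is descriptive.

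**The planned comparisons.** Under Treatment safety, "Additional comparisons across treatment periods for subjects receiving Omegaven® will be aimed to assess occurrence of spontaneous bleeding", together with the maximum triene/tetraene ratio, minimum platelets, maximum INR and pre-albumin trends. The primary safety outcome in that section is a triene/tetraene ratio above 0.2 at any time, compared before and after the start of Omegaven. The Analysis of Safety and Tolerability section adds INR ever above 2 and states: "Comparisons between periods (pre and post-treatment) will be performed based on paired tests". It places significance testing in secondary analyses.

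**The data collection.** Section G says: "Adverse events (AEs) will be assessed and reported from the time of the first Omegaven® infusion until exit from the study". Section E lists what is taken from charts: present illness, past and birth history, examination findings, biopsies, blood chemistries and feeding history. The form described in section B covers laboratory results, nutritional history and biopsies. Neither list names adverse events or bleeding. The Safety Labs Schedule requires triglycerides, coagulation labs and a fatty acid profile at baseline, and repeats each one weekly or monthly during treatment.

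**The concern.** A McNemar test needs the same binary outcome, observed in the same way, in both periods for each child. For clinical events the protocol fixes an on-treatment collection window and no pre-treatment one. The power figures then describe a test that has no specified first half.

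Spontaneous bleeding is the one clinical event named for comparison across periods, and prolonged bleeding time is a recognised risk of the product. If bleeding is actively looked for after the first infusion and known only from incidental chart notes before it, the contrast will tend to show more bleeding on Omegaven whatever the drug does.

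The laboratory outcomes have a milder form of the same fault. A child sampled many times has more chances to cross a limit than a child sampled once. Safety is Aim 1, so a distorted before/after contrast matters even when it is only described.

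**Working it through.** **1. Reproducing Table 4.** Inputs: N = 20, 25, 30; difference d; discordant proportion π. The larger discordant cell is (π + d)/2. Power is the sum, over m ~ Binomial(N, π), of the probability that an exact binomial test on m discordant pairs rejects.

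| d / π | Table 4 (N = 20, 25, 30) | Exact, one-sided 5% | Exact, two-sided 5% |
|---|---|---|---|
| 30% / 40% | 59, 72, 81 | 58.5, 71.6, 81.4 | 45.5, 60.2, 71.3 |
| 30% / 60% | 44, 55, 63 | 43.7, 54.6, 63.4 | 30.6, 41.0, 50.2 |
| 50% / 60% | 92, 97, 99 | 91.9, 97.2, 99.0 | 85.5, 93.7, 97.6 |
| 50% / 80% | 79, 88, 93 | 79.3, 88.0, 93.0 | 68.4, 79.1, 86.6 |

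The 80% rows are about 99% or more either way. The entries are genuine McNemar powers, but they match a one-sided test although the text says two-sided. That is a separate point. It does not affect the argument below.

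**2. Is there a pre-treatment observation?**

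| Outcome | Before treatment | On treatment |
|---|---|---|
| Spontaneous bleeding, other clinical events | no window or source stated | assessed from the first infusion |
| Triene/tetraene > 0.2 | one required baseline profile | at least monthly |
| INR > 2 | one required baseline value | weekly until direct bilirubin is below 2 mg/dL, then monthly |

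In addition, the inclusion criteria admit children already on Omegaven under another protocol. Their baseline at this centre is not an Omegaven-free value.

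**3. Clinical events.** If the pre-treatment period is treated as missing, there are no evaluable pairs and power is undefined. If it were scored as event-free for everyone, all k discordant pairs would point one way and p = 2 × 0.5^k:

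- k = 5: 2 × 0.03125 = 0.0625
- k = 6: 2 × 0.015625 = 0.031

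Six children with any event would therefore be significant. The difference would then equal the discordant proportion, and no row of Table 4 has that pattern. With an assumed on-treatment event probability and no drug effect, P(6 or more children) is:

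| Assumed probability | N = 20 | N = 25 | N = 30 |
|---|---|---|---|
| 10% | 1% | 3% | 7% |
| 20% | 20% | 38% | 57% |
| 30% | 58% | 81% | 92% |
| 40% | 87% | 97% | 99% |

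These are the extreme case. The protocol gives no event rate and does not say that absent records count as no event.

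**4. Laboratory outcomes.** Assume a constant probability q of crossing the limit at each draw, independent draws, one draw before, k draws after, and no drug effect. Then P(before) = q and P(after) = 1 − (1 − q)^k. For q = 10% and k = 6, P(after) = 1 − 0.9^6 = 46.9%. The discordant cells are 0.469 × 0.9 = 0.422 and 0.1 × 0.531 = 0.053, a difference of 36.9 points. Rejection by the two-sided exact test at N = 20, 25, 30:

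| q | k | Ever, before vs after | Rejection |
|---|---|---|---|
| 5% | 3 | 5% vs 14% | 2, 5, 8% |
| 5% | 6 | 5% vs 27% | 24, 38, 50% |
| 10% | 3 | 10% vs 27% | 13, 20, 27% |
| 10% | 6 | 10% vs 47% | 62, 75, 85% |
| 20% | 3 | 20% vs 49% | 34, 45, 55% |
| 20% | 6 | 20% vs 74% | 89, 96, 99% |

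In the last row the difference is 54 points with no drug effect, which is within the size the plan expects to see. Positive correlation between a child's draws would shrink these figures. The values of q and k are assumptions.

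**The case against.** **There is before data.** A reader might infer that the before/after comparison has no pre-treatment data at all. The documents do not support that. Baseline fatty acid, coagulation and triglyceride values are required, and the two binary primary safety outcomes are laboratory values. Hypothesis 1.2 counts coagulopathies among adverse events, so Table 4 may be meant for outcomes such as INR above 2. This stands. It confines the missing-data argument to clinical events and leaves the laboratory outcomes with unequal sampling.

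**Infections and readmissions.** A reader might also infer that any common clinical event will look as if Omegaven caused it, because the Side effects section says that expected events common to these children, "regardless of the type of fat emulsion they receive, include blood stream infections and re-admittance to hospital". But infections are planned as rates after baseline, outside the cross-period list, and readmission is not listed as an outcome in the safety sections. The point reaches only bleeding, the one clinical event named for cross-period comparison.

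**Section G is a reporting rule, and charts exist.** Starting adverse event reporting at the first dose is normal and does not forbid retrospective chart work. Charts are to be reviewed, the department already follows its own short-bowel patients, and the efficacy section uses profiles from two months before baseline. This is fair, and some earlier bleeding may be retrievable. Detailed abstraction rules could also sit in an analysis plan that is not shown. However, the protocol itself fixes the collection window, the items abstracted and the comparison, and these do not fit together. An analysis plan cannot restore events that were not systematically recorded.

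**Low inferential stakes.** Testing is secondary and neither enrolment nor the primary conclusion depends on Table 4. This stands and lowers the severity. It does not remove the fault, because a descriptive before/after contrast carries the same bias.

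**Conclusion.** The point holds in this form. For clinical adverse events, Table 4 states power for a comparison whose pre-treatment half has no specified window or source, and the planned bleeding contrast would be biased against Omegaven by unequal ascertainment. For the triene/tetraene ratio and INR, a pre-treatment value exists, but one required draw is compared with repeated draws for an outcome of the *ever* type. The maximum and minimum values in the cross-period list have the same weakness.

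The size cannot be fixed from the documents. The six-child threshold (p = 0.031) is exact but applies only if the unobserved period is coded as event-free. The rejection probabilities depend on assumed event rates, per-draw probabilities and numbers of draws, and range from negligible to near certain. They show the direction and possible scale of the bias and are not forecasts for this study.

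Severity is moderate, because the primary safety analysis is descriptive and the sample size is not based on power.

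**What to change.** - **Statistical Power and Sample Considerations:** replace adverse events with the named binary laboratory outcome that Table 4 is meant for.
- **Treatment safety, and Analysis of Safety and Tolerability:** limit paired pre/post tests to laboratory outcomes compared over equal windows or equal numbers of draws, for example the baseline value against a single value at a fixed time after day 30. State how children who enter already on Omegaven are handled in these comparisons.
- **Clinical events, including bleeding:** report on treatment only, as rates over follow-up time with exact confidence intervals.
- **If a before/after bleeding contrast is kept:** abstract bleeding from charts with one definition, over pre-treatment and on-treatment windows of equal length, and add this to the items in section E.

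The cost is protocol wording. The optional bleeding contrast adds a short chart abstraction for 20 to 30 children. No treatment or visit changes.

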**Inclusion Criteria:**

1. Patients will be PN dependent (unable to meet nutritional needs solely by enteral nutrition) and are expected to require PN for at least another 30 days.
2. Patients considered eligible for study participation must have parenteral nutrition associated liver disease (PNALD) as defined as a direct bilirubin of  $\geq 2$  mg/dl on at least the last two consecutive measures or by histology and/or currently on Omegaven through another protocol and unable to remain on that protocol due to transfer to our institution. Other causes of liver disease should be excluded. A liver biopsy is not necessary for treatment.
3. The patient must have utilized standard therapies to prevent the progression of his/her liver disease including surgical treatment, cyclic PN, avoiding overfeeding, reduction/removal of copper and manganese from PN, advancement of enteral feeding, and the use of ursodiol (i.e., Actigall®).
4. Patients ages birth up to and including 18 years of age.

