### Duration of Therapy

Patients will remain on Omegaven® until weaned from PN. Patients may continue monotherapy with Omegaven® as an additional source of calories after the dextrose/protein portion of PN is discontinued.

In the event that a patient who has been listed for a liver or liver/intestinal transplant has an organ become available, the participation in this protocol will not preclude them from receiving the transplant.

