### **D. Definition of Primary and Secondary Outcomes/Endpoints**

Generally, primary safety analyses will be based on time from baseline or 30 days after baseline until two months after patients first reached direct bilirubin levels  $< 2$  mg/dL. Baseline will be defined as information collected at the date that treatment starts for Omegaven® patients and on the date that patient reached bilirubin levels  $> 2$  for soybean oil fat emulsion patients. Information on mortality and transplant will be collected during the whole treatment with Omegaven®. Primary efficacy analysis will include time from baseline until the patient normalizes bilirubin (presents three consecutive direct bilirubin  $\leq 2$  mg/dL or a direct bilirubin  $\leq 2$  mg/dL and weaned from TPN).

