#### **Safety Labs Schedule:**

Lab Name	Schedule*
Serum triglycerides	At baseline, weekly for 4 weeks, monthly thereafter
Coagulation labs	At baseline, weekly until direct bilirubin is < 2mg/dL, monthly thereafter
Fatty acid profile	At baseline, monthly thereafter

\*minimum requirements, may be performed more frequently for routine clinical care

If under the discretion of the principal investigator the patient is able to return home and receive Omegaven®, the patient is required to return to Children's Hospital & Medical Center every 2 months or other mutually agreed upon schedule for evaluation and follow up. The Principle Investigator also requires for arrangements to be made through the patient's home health care agency for the required weekly or monthly blood draws the patient will need while at home in order to remain on Omegaven®. The lab results then must be faxed to Children's Hospital & Medical Center in a timely manner. Additionally, measures will be taken to decrease the chance of administration errors when Omegaven® is given in the home. Families will be provided with a letter outlining strategies for reducing medication administration errors, such as independent double-checks.

Dose reduction will occur if there is evidence of lipid intolerance (serum triglycerides  $>$  200mg/dL) or evidence of bleeding. Growth indices include weight, length, and head circumference will also be monitored.

Other standard care laboratory results will be captured for the Omegaven® protocol. These are listed along with the standard schedule in Table 3.

The frequency of laboratory monitoring may be reduced to monthly or as clinically necessary, for patients who have been on a stable regimen of Omegaven® for a minimum of 4 months and whose serum bilirubin and hepatic enzymes have normalized.

The study team will round on all inpatients receiving Omegaven® therapy. A complete comprehensive case review for all inpatients receiving Omegaven® therapy under the compassionate-use protocol and any outpatients issues will be discussed among [name], [name], and the study coordinator. All pertinent medical, nutritional, and psychosocial outpatient information will be reviewed during these case reviews.

[name], Department of Surgery, Children's Hospital & Medical Center  
[name], Department of Surgery, Children's Hospital & Medical Center  
[name], Pediatric Research Office, Dept. of Pediatrics, UNMC  

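### The paired safety comparison counts only from day 30, so children who stop earlier give it no on-drug value; Table 4 makes no allowance for them and does not match its stated two-sided test

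*Protocol*

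**What the plan says.** - **Entry.** Inclusion Criteria, item 1: children must be PN dependent and "are expected to require PN for at least another 30 days".
- **Treatment length.** Duration of Therapy: "Patients will remain on Omegaven® until weaned from PN". Omegaven may continue as a calorie source after the rest of PN stops. The withdrawal list in section G adds unacceptable toxicity, transplant and other reasons.
- **Start of the main window.** Analysis of Safety and Tolerability: "The period receiving Omegaven® will start 30 days after beginning PN with Omegaven® for the main analysis".
- **End of the window, first statement.** Treatment safety: the primary before/after comparison of triene/tetraene ratio above 0.2 runs "one month after treatment started until treatment stopped".
- **End of the window, second statement.** The same subsection then sets follow-up for this and all other safety outcomes by "30 days after treatment started for Omegaven® patients and 2 months after the first direct bilirubin level" below 2 mg/dL. Section D agrees on the end but leaves the start open: "primary safety analyses will be based on time from baseline or 30 days after baseline until two months after patients first reached direct bilirubin levels" below 2 mg/dL.
- **Sampling.** The Safety Labs Schedule gives the minimum for the fatty acid profile: "At baseline, monthly thereafter". The Reversal Study Lab Schedule asks for a weekly panel on Omegaven while direct bilirubin is 2 mg/dL or more.
- **Power.** Statistical Power and Sample Considerations gives Table 4 "assuming 20, 25, or 30 patients" for a two-sided 5% McNemar test. It also says that numbers are not set by power and that the primary safety analysis is descriptive.

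**The concern.** The expected PN time required at entry (30 days) equals the lag before on-drug results count (30 days). A McNemar analysis needs a before value and an after value from the same child. A child who is weaned, transplanted, withdrawn or dies before day 30 has no on-drug after value.

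Two things are at stake. First, the primary fatty acid result may describe only children who stayed on Omegaven for more than a month, with nothing in the text showing how many treated children it leaves out. The same applies to INR above 2, which is a primary safety outcome counted from day 30 and also an example of toxicity leading to withdrawal. A child withdrawn for it in month one can be missing from the analysis meant to show it. Second, Table 4 counts patients where the test counts pairs.

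**Working it through.** **1. Length of the window.** Let T be the day Omegaven stops and B the day of the first direct bilirubin below 2 mg/dL, both counted from the start of Omegaven. Take 2 months as 60 days.

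- First statement (ends when treatment stops): length = max(0, T − 30). For T = 30 this is 30 − 30 = 0 days.
- Second statement (ends 2 months after B): length = max(0, B + 60 − 30). For a child entering with bilirubin of 2 mg/dL or more, B is 0 or later, so at least about 30 days remain whatever T is.
- On-drug part of the second window: max(0, min(T, B + 60) − 30). This is again 0 when T is 30 or less.

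The two statements therefore disagree about calendar time, but under both a child who stops by day 30 has no on-drug time in the window. A child admitted on histology, or transferred while already on Omegaven, may have had B before baseline, which could shorten or empty the second window.

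**2. Can another provision supply the value?**

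- Once off Omegaven, an inpatient with bilirubin of 2 mg/dL or more is scheduled for a PN profile only. Below 2 mg/dL there is one complete post-Omegaven set including fatty acids; it is off drug and not tied to a date after day 30.
- For withdrawn children, the withdrawal text documents measurements up to withdrawal.
- Missing Values interpolates only gaps in the middle of follow-up, so it cannot create a first value after day 30.
- The intention-to-treat rule in the Data Analysis Plan covers temporary discontinuation.

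**3. Reproducing Table 4.** Inputs are the difference d and discordant proportion ψ from Table 4, and n pairs. The number of discordant pairs is m ~ Bin(n, ψ). Given m, the number in the favoured direction is X ~ Bin(m, q), with q = (ψ + d)/(2ψ). Power is the sum, over all m and X, of the probability of outcomes where the exact binomial(m, ½) test rejects. For d = 0.5, ψ = 0.8: q = 1.3/1.6 = 0.8125. For d = 0.3, ψ = 0.4: q = 0.7/0.8 = 0.875.

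| d / ψ | n | Printed | Exact, one-sided 5% | Exact, two-sided 5% |
|---|---|---|---|---|
| 30 / 40 | 20, 25, 30 | 59, 72, 81 | 58.5, 71.6, 81.4 | 45.5, 60.2, 71.3 |
| 30 / 60 | 20, 25, 30 | 44, 55, 63 | 43.7, 54.6, 63.4 | 30.6, 41.0, 50.2 |
| 50 / 60 | 20, 25, 30 | 92, 97, 99 | 91.9, 97.2, 99.0 | 85.5, 93.7, 97.6 |
| 50 / 80 | 20, 25, 30 | 79, 88, 93 | 79.3, 88.0, 93.0 | 68.4, 79.1, 86.6 |

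The 80% difference rows stay at about 99% or more either way. The one-sided exact test matches every printed cell to rounding. No two-sided variant tried (normal approximations, exact, mid-p, chi-square with and without correction, Wald) matched all twelve cells shown. With no loss of pairs, moving to the stated two-sided exact test costs about 1 to 14 points in these rows.

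**4. Effect of losing pairs, on the stated two-sided basis.** The loss is an assumption.

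| Cell | No loss | 10% | 20% | 30% |
|---|---|---|---|---|
| d 50%, ψ 80%, from 20 | 68.4% (20 pairs) | 60.8% (18) | 53.4% (16) | 46.8% (14) |
| d 30%, ψ 40%, from 30 | 71.3% (30 pairs) | 65.0% (27) | 57.6% (24) | 48.8% (21) |

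A 10% loss costs 68.4 − 60.8 = 7.6 points in the first cell and 71.3 − 65.0 = 6.3 in the second.

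**The case against.** A reader might infer that a child who just meets the entry criterion contributes no time at all to the primary safety window. The Protocol does not support that on every reading. Section D and the second statement under Treatment safety let the window run past the end of treatment, and Discontinuation of Therapy keeps children under follow-up for at least 2 months. That part of the objection stands. What remains is narrower: such time is off drug and carries no assured fatty acid value.

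A reader might also infer that lost pairs make Table 4 wrong by a known amount. That is not supported either. Entry selects children expected to need at least 30 more days, so a child with exactly 30 is a boundary case. If the expectation always held, weaning would cost no pairs before day 30. Omegaven may also outlast PN. There is no enrolment target, so the table's sample size can be read as pairs, and no decision rests on it. All of this stands and limits the power side of the point.

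Two further arguments carry part of the way. Adverse events are recorded from the first infusion, deaths and transplants throughout treatment, and withdrawals with reasons, so early failures are not lost to the study. They are still missing from the paired result. Weekly panels at bilirubin of 2 mg/dL or more make sparse sampling a small worry for most children on drug. Finally, denominators and supporting analyses often sit in a SAP, which is not shown; their absence alone would not be a finding. The conflicting window ends and the sidedness of Table 4 are in the Protocol itself.

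**Conclusion.** The point holds in a limited form. Under the wording that ends the window when treatment stops, children who stop before day 30 give no on-drug value to the paired triene/tetraene result, which then describes a selected group. Under the other wording, calendar time may remain but any value would be off drug. Because the primary safety analysis is descriptive, the selection matters more than the power: a proportion can mislead without any test.

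The size of the selection is unknown. The Protocol gives no PN durations, and 0 to 30% is an assumed range, with 0% possible. Table 4 makes no allowance for it. Its one demonstrable overstatement has another cause: the printed values are those of a one-sided 5% exact test. On the stated two-sided basis, the 30%/40% row never reaches 80% (71.3% at 30 pairs), and the 50%/80% row does so only at 30 (86.6%). These figures assume the exact conditional test. The changes are worth making, but nothing here undermines the study's ability to run.

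**What to change.** 1. **Window.** Reconcile section D with the two statements under Treatment safety, so that one start and one end apply to the primary safety comparison.
2. **Reporting.** Keep the day-30 window as the main analysis, but report it against all treated children. Count those with no value after day 30 by reason: weaned, died, transplanted, withdrawn. Add a supporting paired analysis that uses the last on-drug fatty acid profile of children who stop before day 30.
3. **Table 4.** Label the columns as evaluable pairs, recompute all cells on the stated two-sided 5% basis, and revise the accompanying sentences about reaching 80%. If an allowance for lost pairs is shown, state it as an assumption and use the two-sided figures above.

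The entry criterion is unchanged. The cost is Protocol or SAP wording, a less favourable power table and one extra analysis of data already collected, with no added patients or visits. The small downside is that the supporting analysis includes profiles taken before fatty acids have fully turned over, so it should stay secondary.
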